5. GENERAL METHODOLOGY AND CONVENTIONS

The primary analysis will occur after at least 90 FAS participants complete Day 360 (Visit 19) or discontinued from the study prior to Week 52 if they had received Year 1 IP at least

one year prior to the data cutoff. There are 2 options for IAs, both of which are designed to provide data to support an earlier regulatory submission for BLA/MAA as described in [Section 7](#).

As a general rule, all efficacy analyses including the primary endpoint, secondary endpoints, and other endpoints will be conducted based on all FAS participants regardless of adherence to background or protocol mandated glucocorticoid regimens during the first 52 weeks after study drug infusion, unless specified otherwise.

5.1. Hypotheses and Decision Rules

For the primary endpoint, the null hypothesis is that there is no difference between fordadistrogene movaparvovec and placebo with respect to mean change from Baseline at Week 52 in the NSAA total score. The alternative hypothesis is that fordadistrogene movaparvovec is different from placebo with respect to mean change from Baseline at Week 52 in the NSAA total score.

The experiment-wise Type I error rate of $\alpha=0.05$ (two-sided) will be controlled using gatekeeping and fixed-sequence procedures for the primary and select secondary endpoints listed below. The hypotheses for the secondary endpoints are similar to those for the primary endpoint.

- Change from Baseline at Week 52 in the 10 meter run/walk velocity.
- Change from Baseline at Week 52 in the rise from floor velocity.
- Number of skills either improved or maintained at Week 52 based on the individual items of the NSAA.
- Number of skills gained at Week 52 based on the individual items of the NSAA.

If the null hypothesis for the primary endpoint is rejected, statistical testing proceeds to the hypotheses for the secondary endpoints; otherwise, formal statistical testing in the sense of controlling the experiment-wise Type 1 error rate stops and nominal p-values for secondary endpoints will be reported and interpreted accordingly.

The secondary endpoints will be tested in the order specified above. To maintain the study-wise type 1 error rate, the p value boundary for these secondary endpoint analyses will be the same as the primary analysis as detailed in IA SAP. If the null hypothesis for the first endpoint in the sequence is rejected, statistical testing moves to the next endpoint in the sequence. Statistical testing proceeds to subsequent endpoints in the sequence only if the null hypothesis for the previous endpoint is rejected. If a null hypothesis in the sequence is not rejected, formal statistical testing in the sense of controlling the experiment-wise Type I error rate is stopped for all endpoints later in the sequence and nominal p-values will be reported and interpreted accordingly.

The null hypothesis for the primary and secondary endpoints will be tested at Week 52 using the parameter and variance estimates from the mixed model repeated measures (MMRM) model or the generalized mixed model described in [Section 5.2](#).

If either IA is performed, a group sequential approach will be applied to the efficacy analyses to control Type I error rate across the interim analysis/analyses and the primary analysis. Specifically, a gamma family alpha-spending function with gamma parameter -1 will be used. Additionally, an assessment of futility (non-blinding) based on the primary endpoint will be made at each interim analysis, if performed, using a gamma family spending function with gamma parameter -4.

All other statistical tests for secondary endpoints will be performed and the p value boundary for these secondary endpoint analyses will be the same as the primary analysis as detailed in IA SAP. The hypotheses and additional details on decision rules for the two possible IAs will be provided in a separate IA SAP.

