6.2. Secondary Endpoints

6.2.1. Biceps Muscle Biopsies

Endpoints:

- Change from Baseline in percent normal mini-dystrophin expression level in biceps brachii muscle biopsies at Day 360 (Week 52) using an LC-MS assay (primary peptide is LLQV).
- Change from Baseline in percent normal mini-dystrophin expression level in biceps brachii muscle biopsies at Day 360 (Week 52) using an LC-MS assay (supplementary peptide is LEMP).
- Change from Baseline in percent of muscle fibers expressing mini-dystrophin in biceps brachii muscle biopsies at Day 360 (Week 52) as assessed by immunofluorescence.

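### SAP Section 5.1 gives the primary's p-value boundary to five secondary endpoints that lie outside its Type I error strategy

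*SAP*

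**What the plan says.** Section 5.1 does three things in turn.

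- It sets the scope of control. The experiment-wise two-sided 0.05 "will be controlled using gatekeeping and fixed-sequence procedures for the primary and select secondary endpoints listed below". The four listed secondaries are 10 meter run/walk velocity, rise from floor velocity, skills improved or maintained, and skills gained.
- It gives the stopping rules. If the primary is not rejected, formal testing stops and "nominal p-values for secondary endpoints will be reported and interpreted accordingly". Otherwise "The secondary endpoints will be tested in the order specified above", each against the primary's boundary, and the first failure ends formal testing for endpoints later in the sequence.
- After the paragraph on alpha spending it adds: "All other statistical tests for secondary endpoints will be performed and the p value boundary for these secondary endpoint analyses will be the same" as for the primary, with the detail left to the interim analysis SAP.

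Section 3.2 numbers nine secondary endpoints. Taking away the four in the sequence leaves five: LC-MS mini-dystrophin, percent of fibres expressing mini-dystrophin, serum CK, PODCI Transfer and Basic Mobility, and PODCI Sports and Physical Functioning. Sections 6.2.1, 6.2.2 and 6.2.5 provide p-values for all five. None of these sections calls the results nominal or exploratory, although Section 6.4 does label the global statistical test exploratory.

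**The concern.** The four ordered secondaries already have their boundary from the preceding text, so the word *other* most naturally points to the five outside the sequence. In this SAP a p-value boundary is the threshold for rejecting a null hypothesis, and the controlled tests are described in the same terms. A nominal p-value needs no such threshold. The sentence therefore gives a confirmatory decision rule to tests for which the plan offers no error control.

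What is at stake is which claims the plan allows. PODCI matters most: it is a caregiver-reported functional scale, so a chance result there could be presented as support for clinical benefit, having met the trial's own boundary. The primary analysis and the four ordered secondaries are not affected.

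**Working it through.** **Plan's own figure.** The SAP states no error rate for these five tests, so there is none to reproduce on this point. As a check on the design inputs in Section 2.3.1 (difference 3.0, SD 3.5, 99 participants less 3 dropouts, 2:1 allocation), take 64:32 completers:

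- Standard error = 3.5 × √(1/64 + 1/32) = 0.758.
- 3.0/0.758 = 3.96, and power = Φ(3.96 − 1.96) = 97.7%.
- With three looks and the gamma(−1) efficacy bounds, simulated power is 97.1%.

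Both agree closely with the stated 98%.

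**Boundary.** With no interim it is 0.05. With interims, Sections 5.1 and 7 give a gamma(−1) spending function and looks at about 30 and 60 participants. Cumulative two-sided spending is 0.05 × (e^t − 1)/(e − 1). At t = 60/99 = 0.606 this is 0.05 × 0.833/1.718 = 0.0242. Solving for the final look gives these two-sided boundaries:

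| Interims run | Final boundary |
|---|---|
| None | 0.05 |
| First only | 0.043 |
| Second only | 0.037 (0.0368) |
| Both | 0.035 |

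These are my calculations; the interim analysis SAP that fixes the boundary is not shown.

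**Chance of at least one false positive.** For m independent tests at level a it is 1 − (1 − a)^m. For correlated tests I used equicorrelated normal statistics. The SAP gives no correlations, so 0.5 is an assumption.

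| Tests with a true null | Boundary | Independent | Correlation 0.5 |
|---|---|---|---|
| CK and two PODCI scales (3) | 0.05 | 1 − 0.95³ = 0.143 | 0.125 |
| CK and two PODCI scales (3) | 0.0368 | 1 − 0.9632³ = 0.106 | 0.094 |
| All five | 0.05 | 1 − 0.95⁵ = 0.226 | 0.18 |

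The three-test row is the relevant one. Section 3.2 says the immunofluorescence antibody recognises only the transgene protein, and placebo recipients do not receive the transgene in Year 1. A global null that includes the expression endpoints is therefore unlikely. At correlation 0.75 the three-test figures fall to 0.104 at 0.05 and 0.078 at about 0.037.

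**Effect of a gate on NSAA.** Suppose the five are tested only after NSAA is rejected.

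- If NSAA truly has no effect, a false claim first needs a false rejection of NSAA, so the gate keeps the error rate within 0.05.
- If NSAA has the planned effect, the gate is open about 98% of the time. The chance of a false claim among the three at 0.05 is then at least 0.143 − 0.02 = 0.123 if they are independent, or 0.125 − 0.02 = 0.105 at correlation 0.5. This holds whatever their correlation with NSAA.

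The gate protects only where NSAA itself is null.

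**The case against.** The strongest reply is that the sentence is loose but harmless when read with the rest of Section 5.1.

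- **A primary gate may exist.** The primary-failure clause speaks of secondary endpoints without restriction, so it can be read as making all of them nominal when NSAA fails. A reader might infer that CK or PODCI could be declared positive after a failed NSAA. The document does not support stating that as fact. The gate is uncertain: the next paragraph ties *the secondary endpoints* to the listed order, and the later sentence carries no condition.
- **No control was claimed.** A reader might also infer that the stated experiment-wise 0.05 is broken. It is not, because the SAP limits that claim to the primary and the four listed endpoints. The version history in Appendix 6 records that the PODCI endpoints were taken out of the controlled set, which suggests the sponsor meant them to be outside it. That intention makes it harder to justify giving them the primary's boundary.
- **P-values are marked unadjusted.** Sections 5.2.1.1 and 5.2.1.3 say so. But the wording in 5.2.1.1 also covers the primary and both velocity endpoints, so it does not mark these tests as non-confirmatory.
- **The sentence may only carry the interim-adjusted threshold across.** This is plausible from its position. It means that *full alpha* holds only if no interim is run.
- **The biopsy endpoints may not be meant.** Section 5.1 tests its hypotheses by MMRM or the generalized mixed model, whereas biopsies use ANCOVA. This has some weight and is a further reason to rest on CK and PODCI.
- **Larger counts are not supported.** LEMP is called a supplementary peptide and is not a numbered secondary, so a sixth test should not be counted. Reading the sentence as covering all nine secondaries conflicts with the word *other*.

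What survives is that, even with an NSAA gate, the five tests have no order, no shared alpha and no link to whether the sequence is still open.

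**Conclusion.** The point holds as a defect in the decision rule: a confirmatory boundary is attached to tests that the plan leaves uncontrolled. It does not show that the controlled family loses its 0.05 protection, nor that the five can certainly be claimed when NSAA fails.

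For the three endpoints with a plausible null, a false positive somewhere among them is about 2.5 to 2.9 times as likely as 0.05 (0.125/0.05 and 0.143/0.05) if no interim is run, and about twice as likely (0.094/0.05 = 1.9 and 0.106/0.05 = 2.1) if only the second is run. This rests on an assumed correlation of 0 to 0.5, on CK and both PODCI nulls being true, and on boundaries calculated without the interim analysis SAP. The all-five figures are an upper case under an unlikely global null.

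**What to change.** Replace the closing sentence of Section 5.1 with text such as:

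> Secondary endpoints not in the fixed sequence are outside the Type I error strategy; their p-values are nominal, are not compared with any boundary, and support no claim of statistical significance.

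State also that the primary's boundary applies only to the four ordered secondaries, and only while the sequence is open. If a formal PODCI claim is wanted, append both scales to the end of the sequence before unblinding.

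The cost is a short wording change, with no effect on models, data or sample size. The sponsor gives up the ability to call these endpoints significant on their own.

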5.2. General Methods

A general description of how the study will be summarized including definitions of treatment groups and reporting period is provided in [Section 2.3.2](#).

5.2.1. Analyses for Continuous Endpoints

5.2.1.1. Mixed Model Repeated Measures (MMRM)

The MMRM model assumes that all random effects in the model are normally distributed. The dependent variable will be the specific endpoint and the model will include fixed effects terms for:

- Treatment group (as a categorical variable);
- Scheduled visit time point (as an ordered categorical variable);
- Interaction between treatment group and scheduled visit time point.

Additional fixed effects (eg, covariates and interaction effects) to be included in the model for specific analyses are given in [Section 6](#). Participant will be the random effect in the model. The restricted maximum likelihood (REML) estimation method will be used with an unstructured covariance matrix to describe the correlation among different visits from the same participant. If there are convergence issues with the model, the following structures will be considered in the order listed below until convergence is obtained:

1. Spatial Power (SP);
2. Autoregressive-1 (AR(1));
3. Compound Symmetry (CS).

The Kenward-Roger degrees of freedom will be used.

The model-adjusted estimates for the endpoint for each treatment group at each specified time point will be provided using the least squares (LS) means calculated based on the average continuous covariate values, standard error of each LS mean, and their 95%

confidence intervals (CIs). The difference in LS means (fordadistrogene movaparovec minus placebo) will be provided at each specified time point along with corresponding standard error, two-sided p-values (unadjusted for multiplicity), and 95% CIs (unadjusted for multiplicity).

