2.3. Study Design

This is a Phase 3, global, multi-center, randomized, double-blind, placebo-controlled study to assess the safety and efficacy of fordadistrogene movaparvovec gene therapy in approximately 99 ambulatory male participants (in the FAS; see [Section 4](#)), ages ≥ 4 to < 8 years, with a genetic diagnosis of DMD who are on a stable daily regimen of glucocorticoids.

Eligible participants will be randomized into Cohort 1 or Cohort 2 in a 2:1 fashion and stratified by their age at Screening (< 6 or ≥ 6 years old). Study enrollment will be managed to ensure that no more than 55% of dosed participants are in either of the Screening age stratum. Enrollment will be assessed periodically, and if an imbalance is noted, enrollment of the overrepresented stratum may be paused until a more balanced distribution is achieved. In the context of this study, treatment will consist of two single intravenous infusions, one of fordadistrogene movaparvovec and one of placebo, with the timing and sequence as described below:

- Cohort 1 (approximately 66 participants): will receive a single dose of fordadistrogene movaparvovec on Day 1 (Visit 3) and a single dose of placebo at Day

DMB02-GSOP-RF02 4.0 Statistical Analysis Plan Template 01-Nov-2018

PFIZER CONFIDENTIAL

Page 14

TMF Doc ID: 98.03

390 (Visit 20). They will be followed for 5 years after the administration of the single dose of fordadistrogene movaparvovec. Total time on study will be approximately 5 years.

- Cohort 2 (approximately 33 participants): will receive a single dose of placebo on Day 1 (Visit 3) and a single dose of fordadistrogene movaparvovec at Day 390 (Visit 20), if they remain eligible. They will be followed for 5 years after the administration of the single dose of fordadistrogene movaparvovec. Total time on study will be approximately 6 years.

Figure 1. Study Schema

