2.3.1. Sample Size Determination

The sample size of 99 participants in the FAS (see Section 4) is based on the primary efficacy endpoint of change from Baseline at Week 52 in the NSAA total score. The above sample size (assuming 3 participants will drop out of the study prior to Week 52) will provide 98% power to detect a treatment difference (fordadistrogene movaparvovec minus placebo) of 3.0. These calculations are based on $\alpha=0.05$ (two-sided), a 3-look group-sequential design with a gamma family (-1) spending function to determine the efficacy boundary, a gamma family (-4) spending function for the non-binding futility boundary, a common standard deviation of 3.5, and using the normal approximation of the test statistic for the comparison between two means.

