Appendix 5.2. Sample SAS Code for The Primary Analysis with Spatial Power Covariance

```
proc mixed data=nsaa_pb;

  class subjid trt01pn visitn;

  where avisit in ("Week 9" "Week 18" "Week 35" "Week 52") & param = 'NSAA Total
Score';

  model chg = trt01pn base agemodel visitn trt01pn*visitn base*visitn agemodel*visitn/
DDFM=KenwardRoger;

  repeated visitn/ type= SP(POW)(visitn) subject=subjid ;

  lsmeans trt01pn*visitn/ diff alpha=0.05 CL ;

  lsmestimate trt01pn*visitn 'LSM Difference at Week 52' 0 0 0 1 0 0 0 -1/alpha=0.05 cl;

run;
```

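### Every fallback covariance structure for the MMRM assumes equal variance at all visits; if the unstructured fit fails and variance grows toward Week 52, the Week 52 standard error is too small

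*SAP*

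**What the plan says.** SAP Section 5.2.1.1 specifies REML, an unstructured covariance and Kenward-Roger degrees of freedom. If there are convergence problems, "the following structures will be considered in the order listed below until convergence is obtained", and the list is spatial power, AR(1), compound symmetry. Appendix 5.2 codes the first fallback as "repeated visitn/ type= SP(POW)(visitn) subject=subjid", with `visitn` also in the CLASS statement. Neither place offers a heterogeneous-variance structure or a robust standard error.

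The primary model (Section 6.1.1.1) uses Weeks 9, 18, 35 and 52, with baseline and age each crossed with visit. Section 5.1 tests the hypotheses at Week 52 and controls the experiment-wise error rate at two-sided 0.05. The only variability figure is in Section 2.3.1, "a common standard deviation of 3.5", used for the Week 52 change. No SD is given for the earlier visits.

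**The concern.** The formal test concerns one visit, the last. A structure with one common variance estimates that visit's variance from all visits pooled. If change from baseline is less variable early than late, the pooled figure is below the Week 52 figure and the test statistic is too large. Kenward-Roger corrects for small-sample estimation of the covariance parameters; it does not repair a wrong structure.

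Rising variance is a reasonable expectation here. The disease is progressive, and Sections 2.2.1 and 2.2.2 set the NSAA score and the two velocities to 0 after death, and after loss of ambulation if the test is not done. Such zeros can only accumulate over follow-up.

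At stake is the 0.05 commitment in Section 5.1, if a fallback is ever used for the primary endpoint or for the two velocity endpoints in the fixed sequence, and the reliability of standard errors elsewhere.

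**Working it through.** **Inputs from the SAP.** "The sample size of 99 participants in the FAS", 2:1 allocation (66:33), "assuming 3 participants will drop out of the study prior to Week 52" (so 96, taken as 64:32), difference 3.0, SD 3.5, two-sided alpha 0.05, gamma(-1) efficacy spending, looks at about 30 and 60 completers. Target days are 60, 120, 240 and 360 (Appendix 2.1).

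**The plan's own figure.** The SAP says the design "will provide 98% power to detect a treatment difference (fordadistrogene movaparvovec minus placebo) of 3.0". In a fixed design with 99, SE = 3.5 × √(1/66 + 1/33) = 0.746, and power = Φ(3.0/0.746 − 1.96) = Φ(2.06) = 98.0%. With 96 it is 97.7%. With three looks, ignoring the non-binding futility bound, it is 97.4% (99) or 97.1% (96). The stated figure is reproduced to within a point and is not in dispute.

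**Formula for the fallback.** With complete data and every covariate crossed with visit, the Week 52 estimate is the same under any covariance structure; only its standard error changes. Under compound symmetry the REML variance is the average of the visit variances, so

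SE ratio = √(mean of the four visit variances) / (SD at Week 52)

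type I error = 2 × [1 − Φ(1.96 × SE ratio)]

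**Scenario A: a share f of the Week 52 variance accumulates linearly with time (assumption).** The mean of day/360 is (60 + 120 + 240 + 360)/(4 × 360) = 0.542.

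- f = 1: ratio = √0.542 = 0.74, type I error about 15%.
- f = 0.25: ratio = √(0.75 + 0.25 × 0.542) = 0.94, type I error about 6.5%.

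Across all three structures the fitted SDs were 2.58 to 2.67 (f = 1) and 3.29 to 3.33 (f = 0.25), against 3.5. Ratios therefore run from 0.74 to 0.95 and type I error from about 15% to 6%.

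**Scenario B: assumed visit SDs.** The formula was checked by simulation under the null: 99 participants, three random dropouts, REML fits of all three fallbacks, t reference with 92 df, 2,000 runs per row (5,000 for the equal row). At a true 5% the Monte Carlo error with 2,000 runs is √(0.05 × 0.95/2000) = 0.005.

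| SD at Weeks 9/18/35/52 | Ratio, formula (CS) | Type I, formula | Type I, simulated fallbacks |
|---|---|---|---|
| 3.5/3.5/3.5/3.5 | 1.00 | 0.050 | 0.053 |
| 2.5/2.8/3.2/3.5 | 0.86 | 0.090 | 0.086–0.092 |
| 2.0/2.5/3.0/3.5 | 0.80 | 0.116 | 0.106–0.114 |
| 1.5/2.0/2.8/3.5 | 0.73 | 0.151 | 0.117–0.138 |
| 3.5/3.2/2.9/2.6 | 1.18 | 0.021 | 0.016–0.019 |

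A Week 52-only ANCOVA, standing in for a separate Week 52 variance, gave 0.044 to 0.054 in every row. No heterogeneous structure was fitted directly.

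**Scenario C: one late zero (assumption).** Take SD 3.5 at every visit, and let one boy in 99 be set to 0 only at Week 52, an extra change of −15 to −20. The added variance is (1/99)(98/99) × 15² = 2.25, or × 20² = 4.00. For the first, the ratio is √[(3 × 12.25 + 14.50)/4 / 14.50] = 0.94; for the second, √[(3 × 12.25 + 16.25)/4 / 16.25] = 0.90. Type I error is about 6.5% to 7.7%.

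**How likely the fallback is.** The unstructured matrix has 4 × 5/2 = 10 parameters for four visits and 8 × 9/2 = 36 for the eight CK visits in Section 6.2.2. The region models (Section 6.5.3) have 16 fixed effects plus 10 covariance parameters, on about 99/3 = 33 boys each if evenly split. Section 7 applies the main-analysis method to interims, the first at about 30 completers.

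**The case against.** The strongest reply is that the SAP already has an ordered, pre-specified rule that starts with the right structure, and that it would rarely be left where it matters most. Ten covariance parameters for about 99 boys should converge. Where failure is more likely, little controlled alpha is at risk: CK and the subgroups are outside the fixed sequence, and the SAP says nothing about how the variance of log CK changes over the year. All of this stands and limits the weight of the point. The early interim is the main exception, since alpha would be spent there; its details are in a separate interim SAP that is not at hand.

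A reader might go further in three ways that the SAP does not support:

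- **That any fallback inflates type I error.** It does so only if the Week 52 variance exceeds the pooled variance, and no visit-level SDs are given.
- **That the global statistical test is inflated.** Its p-value comes from permutation (Section 5.2.4). A mis-scaled standard error affects observed and permuted statistics alike if the same rule is applied each time, so the p-value is not affected.
- **That Appendix 5.2 wrongly reduces spatial power to AR(1).** This holds, for positive correlation, if `visitn` is coded 1 to 4. The coding is not stated, and the Week 52 contrast needs only four ordered levels.

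**Conclusion.** The point holds in conditional form. All listed fallbacks impose equal variance across visits. If the unstructured fit fails and variance rises toward Week 52, the Week 52 standard error is about 0.74 to 0.95 of its true value and two-sided type I error is about 6% to 15% at nominal 5%. The upper end requires all of the variance to accumulate over time, with no constant component such as measurement noise; the simulated rising patterns gave about 0.09 to 0.14.

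The sizes rest on assumed SDs before Week 52 and use the NSAA SD, so they do not carry over to CK. The simulation used a t reference rather than Kenward-Roger. This is a weakness in a contingency rule that is cheap to remove, not evidence that the planned primary test is invalid.

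**What to change.** In Section 5.2.1.1, after unstructured and before any homogeneous structure, list heterogeneous Toeplitz (TOEPH), then ARH(1), then CSH, each with Kenward-Roger. If spatial power is kept, Appendix 5.2 should use a numeric study-day coordinate (60, 120, 240, 360) held in a variable separate from the CLASS visit variable.

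The cost is SAP wording and code, made before unblinding. With four visits TOEPH has 4 + 3 = 7 parameters and ARH(1) and CSH have 4 + 1 = 5, against 2 for the present fallbacks and 10 for unstructured. For eight CK visits the counts are 15, 9 and 9, against 36. One drawback is that TOEPH and ARH(1) index correlation by visit order, not by actual spacing.

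A sandwich variance should not be the default unless a small-sample correction is specified, because the fallback is most likely in small subgroups, where an uncorrected sandwich can itself understate the standard error.
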